### **Duration by Period**

Overall duration (in days) of each treatment received within each study period will be calculated. Duration within each period is defined for each treatment group as:

*Last dose date in period – first dose date in period + 1*

#### **6.3.4.2 Summary of Dosing**

The number of doses taken for each subject for each period will be determined using the eCRF drug accountability data and is defined as:

*Doses Taken: (number of tablets dispensed – number of tablets returned)*

The number of doses taken will be summarized descriptively by treatment group within each period and overall.

#### **6.3.4.3 Compliance**

Treatment compliance will be determined from data captured on the Drug Accountability eCRF.

*Number of expected doses: (date of next visit – date of current visit) x 3*

[figure not shown]
Treatment compliance will be derived for each period. Compliance is defined as:

$$\left( \frac{\text{Number of doses taken}}{\text{Number of expected doses}} \right) \times 100$$

Period compliance will be calculated by summing over all visits within the period using descriptive statistics by treatment group. The number and percentage of subjects with <75%, 75% to 100%, and >100% compliance will be provided by treatment group for each period. If a subject does not return the container, then this dispensation event will be excluded in the calculation for the total number of doses taken, total number of expected doses, and total compliance.

Sponsor: Bristol-Myers Squibb

Protocol no: IM011046

## 6.6 Statistical Impacts Due to COVID-19

### 6.6.1 Impact on Efficacy Endpoints

There are no COVID-19-related impacts to the Week 16 and Week 24 endpoints as all subjects remaining in the trial completed these visits prior to COVID-19 restrictions. Key secondary efficacy endpoints involving later visits may be impacted by COVID-19 in the form of missing data and/or a treatment assignment defaulting to BMS-986165. If a subject has missing data or is switched to BMS-986165 from a different treatment due to COVID-19 during the Week 24 through Week 52 period, the subject will be excluded from the analysis.

Key secondary efficacy endpoints that may be impacted include the following:

- sPGA 0/1 response at Week 52 and at Week 24
- PASI 75 response at Week 52 and at Week 24
- PASI 90 response at Week 52 and at Week 24

A sensitivity analysis will also be performed for the above endpoints using the last observed value. The data handling rules to be used are as follows for subjects with missing data or for those subjects who switch to BMS-986165 from a different treatment due to COVID-19:

- If the subject is missing the Week 52 response value (ie, sPGA 0/1, PASI 75, PASI 90), then the last observed response value during the Week 24 through Week 52 period will be carried forward to the Week 52 value
- If the subject is switched to BMS-986165 from a different treatment due to COVID-19, then the last observed response value prior to the switch will be carried forward to the Week 52 value

Censoring rules will be applied to the time to first loss endpoints evaluated for the maintenance of efficacy of BMS-986165 through Week 52 in subjects who were originally randomized to BMS-986165 and impacted by COVID-19-related issues post Week 24:

- Subject has missing visits (ie, efficacy assessments not performed) after Week 24 and assuming loss of response was not observed prior to missing visits:

Sponsor: Bristol-Myers Squibb  
Protocol no: IM011046

- If the subject returns at a later visit and is found to have had a loss of response, midpoint imputation will be used to determine time to first loss (ie, midpoint of the censoring interval).
- If the subject returns at a later visit and has not had a loss of response, then the subject will continue to be evaluated for time to first loss.
- If the subject is discontinued from the study treatment, then the subject will be censored at the time of study treatment discontinuation.

Time to first loss endpoints include:

- Time to first loss of PASI 75 among subjects that are PASI 75 responders at Week 24
- Time to first loss of sPGA 0/1 among subjects that are sPGA 0/1 responders at Week 24 where loss of sPGA 0/1 is defined as an sPGA score  $\geq 2$  (sPGA scores are rounded to the nearest whole number)

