#### Week 16 activities

The coprimary endpoints, static Physician Global Assessment (sPGA) 0/1 and Psoriasis Area and Severity Index (PASI) 75 will be assessed at Week 16. Subjects receiving placebo will be switched in a blinded manner to BMS-986165 6 mg QD at Week 16. Subjects who are randomized to BMS-986165 6 mg QD or apremilast will continue on their assigned treatment regimen in a blinded manner.

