### Week 24 activities

[figure not shown]
At Week 24, subjects originally randomized to apremilast who do not achieve PASI 50 response will be switched in a blinded manner to BMS-986165 6 mg QD. Subjects in the apremilast treatment arm who achieve PASI 50 response at Week 24 will continue to receive apremilast in a blinded manner through Week 52.

During the Week 24 assessment, a subject who has an sPGA  $\geq 3$  or ss-PGA $\geq 3$  may be treated with restricted topicals/shampoos as described in the protocol (Section 6.7.1). These treatments may only be initiated at Week 24, and not at subsequent time points. A subject who is provided these treatments at Week 24 may use them as needed per the investigator's judgement through Week 52.

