#### Imputation Methodology for Week 24 Endpoints (for comparison of BMS-986165 6 mg QD to apremilast)

NRI will be used for key secondary efficacy endpoints for subjects who:

- Discontinue treatment or study prior to Week 24
- Have missing Week 24 endpoint data for any reason

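### The COVID-19 exclusion in SAP 6.6.1 drops Week 24 nonresponders whose result is already known, and its switch part can remove only subjects still on apremilast; the likely effect is small and the fix is cheap

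*SAP*

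**What the plan says.** SAP 6.1.2.1 counts a subject as a responder on the three Week 52 endpoints only if the criterion is met at Week 24 and again at Week 52. It applies nonresponder imputation (NRI) to discontinuation before Week 52, to missing Week 24 or Week 52 data, and to apremilast subjects moved to BMS-986165 at Week 24 for lack of PASI 50.

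SAP 6.6.1 adds a COVID-19 rule for the same endpoints. It states that, for Weeks 16 and 24, "all subjects remaining in the trial completed these visits prior to COVID-19 restrictions". It expects later problems to be missing data or "a treatment assignment defaulting to BMS-986165". A subject with missing data, or moved to BMS-986165 from another treatment, is left out: "due to COVID-19 during the Week 24 through Week 52 period, the subject will be excluded from the analysis". A sensitivity analysis instead carries the last observed response forward to Week 52. One of its rules begins "If the subject is missing the Week 52 response value"; the other uses the last value before a COVID-19 switch.

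SAP 2.1 fixes who takes what after Week 24. "Subjects receiving placebo will be switched in a blinded manner to BMS-986165 6 mg QD at Week 16". Apremilast subjects without PASI 50 move to BMS-986165 at Week 24. "Subjects in the apremilast treatment arm who achieve PASI 50 response at Week 24 will continue to receive apremilast".

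**The concern.** The exclusion does not depend on Week 24 response. It therefore discards outcomes that need no assumption, including those of apremilast subjects switched by design, whom 6.1.2.1 already scores as nonresponders. Its switch part also acts on one randomised arm only. Both are post-randomisation exclusions from the main analysis of three active-comparator endpoints in a branch tested at two-sided 0.025. At stake are some precision and a possible shift in the estimated difference from apremilast.

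**Working it through.** The plan states no COVID-19 counts and no response rates for these endpoints, so there is no figure to reproduce. The logic comes from the text; every rate below is an assumption.

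**1. Settled outcomes.** Composite = R24 × R52. If R24 = 0 the composite is 0 whatever R52 is. If R24 = 1 it may be 0 or 1. Only Week 24 responders are unsettled when Week 52 is missing.

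**2. Who can meet the switch condition after Week 24.**

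| Group | Taking after Week 24 | Can be switched to BMS-986165? |
|---|---|---|
| Randomised to BMS-986165 | BMS-986165 | No |
| Randomised to placebo | BMS-986165 | No |
| Apremilast, no PASI 50 | BMS-986165 | No |
| Apremilast, PASI 50 | apremilast | Yes |

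By-design switchers are nonresponders under 6.1.2.1, so any apremilast composite responder must be in the last row.

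**3. Assumed inputs.** About 600 subjects at 2:1:1 gives 300 on BMS-986165 and 150 on apremilast. Week 24 response 65% vs 40%; Week 52 response among Week 24 responders 80% vs 75%. Composite: 0.65 × 0.80 = 52% and 0.40 × 0.75 = 30%; difference 22.0 points.

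**4. Missing-data part, random missing share m in both arms.** At m = 10%, settled nonresponders are 300 × 0.10 × 0.35 = 10.5 of 30 dropped on BMS-986165 and 150 × 0.10 × 0.60 = 9 of 15 on apremilast. The expected rates do not change.

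- Variance per arm under exclusion: p(1−p)/[n(1−m)].
- Variance per arm with settled outcomes kept and Week 52 estimated from observed Week 24 responders: p52²·p24(1−p24)/n + p24·p52(1−p52)/[n(1−m)].
- At m = 10%, exclusion: 0.2496/270 + 0.21/135 = 0.002480, SE 4.98 points.
- At m = 10%, kept: (0.000485 + 0.000385) + (0.000900 + 0.000556) = 0.002326, SE 4.82 points. Variance ratio 1.066.
- The same ratio is 1.013 at 2%, 1.032 at 5% and 1.142 at 20%.
- Power, Φ(0.22/SE − 2.241), is 0.985 under exclusion and 0.990 with outcomes kept at m = 10%.

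Bias needs response-related missingness. Suppose it occurs in the apremilast arm only. With 20% of Week 24 responders and 5% of nonresponders missing, the rate is 0.24/(0.32 + 0.57) = 27.0%, difference 25.0. Reversed, it is 0.285/(0.38 + 0.48) = 33.1%, difference 18.9. The direction is not fixed.

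**5. Switch part.** Let q be the share of the apremilast arm with PASI 50 at Week 24 (assumed 60%) and s the share of those switched for COVID-19, unrelated to response. Without switching the rate is 30%. Exclusion gives 0.30(1−s)/(1−qs); NRI gives 0.30(1−s).

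| s | Removed (150qs) | Rate, exclusion | Difference | Rate, NRI | Difference |
|---|---|---|---|---|---|
| 5% | 4.5 | 29.38% | 22.6 | 28.5% | 23.5 |
| 10% | 9 | 28.72% | 23.3 | 27.0% | 25.0 |
| 20% | 18 | 27.27% | 24.7 | 24.0% | 28.0 |

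For q from 50% to 70%, the exclusion difference at s = 10% runs from 23.6 down to 23.0. With lower composite rates (33.75% vs 16.25%, difference 17.5) it is 18.2 at s = 10%. Removing a single switched subject moves 30.0% to 29.9%.

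**The case against.** The best defence has four parts.

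- **The rule is authorised.** SAP 6.1 lets an analysis depart from the FAS where stated. The Week 24 NRI bullet reads "Have missing Week 24 endpoint data for any reason", while the Week 52 bullet has no such any-reason wording. So 6.6.1 is best read as the specific rule for COVID-19 cases, not as a contradiction. That stands, although precedence is left to inference.
- **The direction depends on the benchmark.** A reader might infer that the rule favours BMS-986165. It does so only against the response that switched subjects would have had without the switch. Against NRI, which 6.1.2.1 uses for by-design switchers and missing data, exclusion favours apremilast: 23.3 against 25.0 points at 10% switched. That stands, and an unqualified claim of bias is not supported.
- **Complete-case exclusion is defensible under random missingness, and a sensitivity analysis is planned.** The last-observed-value analysis retains affected subjects under both parts of the rule. It is not the main analysis, so it mitigates the problem only in part.
- **No scenario above changes a conclusion.** True, and all inputs are assumed.

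Three further readings are tempting but weak. One is that a single missed visit between Weeks 28 and 48 excludes a subject with Weeks 24 and 52 observed. The endpoints use only those two weeks and the sensitivity rule names the Week 52 value, so this is strained; a clarifying phrase is enough. Another is that the change was made silently. SAP 2.5 lists important changes only, and the document history records 6.6 as a new section. The third is that COVID-19 discontinuation has no rule for these endpoints. The text "If the subject is discontinued from the study treatment, then the subject will be censored at the time of study treatment discontinuation" does belong to the time-to-loss endpoints, but 6.1.2.1 lists discontinuation without limiting the reason, so only precedence needs stating.

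**Conclusion.** The point holds in a limited form. Week 24 nonresponders are known nonresponders and need not be dropped; under random missingness, dropping them makes the variance about 1 to 7% larger at 2 to 10% missing. The switch part can remove only apremilast-arm PASI 50 responders still on apremilast. It lowers the apremilast rate by about 0.6 to 1.3 points at 5 to 10% switched, relative to response without the switch and if switching is unrelated to response among them. Relative to NRI it raises that rate. With few switches it is negligible.

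These sizes rest on assumed rates, and the documents give no COVID-19 counts. Section 6.1.3 is not shown, so the place of these endpoints in the testing order is not judged. This is a change to consider, not a flaw that threatens the study's conclusions.

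**What to change.** Replace the exclusion sentence in 6.6.1 with wording such as:

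> All FAS subjects stay in the main analysis. Week 24 nonresponders, and subjects switched by design at Week 24, are nonresponders. For a Week 24 responder who has not discontinued, and whose Week 52 value is missing because of COVID-19 or who was moved to BMS-986165 because of COVID-19, Week 52 response is multiply imputed by randomised arm from response at visits before any switch. The collapsed strata of 6.1 are used where cells are sparse. Discontinuations and other missing data follow 6.1.2.1. For the cases named here, this section takes precedence over 6.1.2.1.

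Report full-FAS NRI as a sensitivity analysis and keep the last-observed-value analysis. Cross-references from 6.1.2.1 and Appendix 1 are housekeeping.

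**Cost.** SAP wording, and an extension to Week 52 of the multiple imputation that 6.1.1.2 plans for Week 16. Sparse cells need care: China has no apremilast arm, and the SAP expects small samples in China and Japan. The method assumes that Week 52 response is missing at random given arm and earlier response. NRI for COVID-19 discontinuations is conservative. If a share d of Week 24 responders in both arms discontinues for that reason, the difference is 22.0(1−d): 20.9 at 5% and 19.8 at 10%.

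**Alternative without a new program.** Make the last-observed-value rule already in 6.6.1 the main analysis. It carries Week 24 to 48 response forward, so it tends to overstate Week 52 response in affected subjects. At 10% missing, if every value is carried from Week 24, the rates are 0.65(0.9 × 0.80 + 0.1) = 53.3% and 0.40(0.9 × 0.75 + 0.1) = 31.0%; difference 22.3.

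**Avoid the half-measure** of keeping settled nonresponders while still dropping affected Week 24 responders. It biases both rates downward: at 10% missing, 0.468/0.935 = 50.1% and 0.27/0.96 = 28.1%, instead of 52% and 30%.

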#### **9.4.4 Time-to-Event Endpoints**

The Kaplan-Meier product limit method will be used to estimate the distribution curve for time-to-loss (from Week 24) of PASI 75 response for the BMS-986165 treatment group.

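### COVID-19 censoring at treatment discontinuation counts unassessed time as maintained response when no early-discontinuation sPGA/PASI was done, so the BMS-986165 time-to-first-loss curves are somewhat too high

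*SAP*

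**What the plan says.** SAP 6.6.1 sets COVID-19 rules for time to first loss "in subjects who were originally randomized to BMS-986165 and impacted by COVID-19-related issues post Week 24". The triggering situation is: "Subject has missing visits (ie, efficacy assessments not performed) after Week 24 and assuming loss of response was not observed prior to missing visits". Three outcomes follow.

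- The subject returns and has lost response: "midpoint imputation will be used to determine time to first loss", placing the event in the middle of the unobserved interval.
- The subject returns and has not lost response: evaluation continues.
- The subject stops study treatment: "then the subject will be censored at the time of study treatment discontinuation".

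Two endpoints are named: "Time to first loss of PASI 75 among subjects that are PASI 75 responders at Week 24" and "Time to first loss of sPGA 0/1 among subjects that are sPGA 0/1 responders at Week 24", with loss of the latter defined as an sPGA of 2 or more. For the estimator, Protocol 9.4.4 states: "The Kaplan-Meier product limit method will be used to estimate the distribution curve for time-to-loss (from Week 24) of PASI 75 response", for the BMS-986165 group.

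Protocol Table 3 schedules sPGA and PASI every four weeks from Week 24 to Week 52, and the Week 52 column doubles as the early-discontinuation visit. Protocol 4.1.5, 7.1 and 7.1.2 ask subjects who stop treatment to remain in the study for scheduled procedures.

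**The concern.** A subject's response status is known only up to the last sPGA or PASI performed. If visits are missed and treatment then stops without a further assessment, status during the gap is unknown. Censoring at the stop date nevertheless keeps the subject in every Kaplan-Meier denominator up to that date, and the subject cannot contribute an event. Denominators grow while event counts do not, so each step down is too small and the curve sits too high.

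The first rule in the same list dates a loss found after such a gap to its midpoint, so the SAP accepts that losses occur inside gaps. The third rule treats the whole gap as loss-free.

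At stake is the description of how well response to BMS-986165 is maintained from Week 24 to Week 52.

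**Working it through.** **Inputs from the documents.** Four-weekly assessments from Week 24 to Week 52 (Protocol Table 3); a BMS-986165 arm of about 600 × 2/4 = 300 (Protocol 4.2); Kaplan-Meier estimation (Protocol 9.4.4). The documents give no number of Week 24 responders, loss rate or count of affected subjects, so there is no plan figure to reproduce. Everything else below is assumed.

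**Formula.** S(t) = product over event times of (1 − d/n), where d is losses and n is subjects still at risk. The two rules differ only in how long an affected subject stays in n.

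**1. Worked example.** Take 100 Week 24 responders. Ninety are fully observed, with 3 losses at each of the 7 visits from Week 28 to Week 52. Ten are last assessed at Week 32, have no later assessment, and stop treatment at Week 46.

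- SAP rule: the ten count at Weeks 28-44 (15 losses among 100), then leave. S(52) = (85/100) × (69/75) = 78.2%.
- Censoring at last assessment: the ten count at Weeks 28 and 32 only. S(52) = (94/100) × (69/84) = 77.2%.
- The 90 fully observed subjects alone: 69/90 = 76.7%.

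The two rules differ by 1.0 point.

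**2. Simulation.** Assumed 180 Week 24 responders, 200 runs per scenario, constant hazard of loss. Affected subjects are last assessed at a visit between Week 24 and Week 40 and stop 4 to 12 weeks later with no assessment. Entries are the SAP-rule estimate minus the last-assessment estimate at Week 52, in percentage points, when affected subjects lose response at the same rate as others.

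| Affected | 85% true maintenance | 70% true maintenance |
|---|---|---|
| 2% | 0.06 | 0.11 |
| 5% | 0.15 | 0.28 |
| 10% | 0.31 | 0.60 |
| 20% | 0.65 | 1.20 |

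In these scenarios last-assessment censoring was within about 0.2 points of the true value. When affected subjects lost response at twice the rate (20% affected, 70% baseline), the true value was 66.1%, the SAP rule gave 69.9% and last-assessment censoring 68.7%. Both are too high, the SAP rule more so.

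**3. Dependence on the stop time.** Assume 130 subjects at risk at Week 36 and a 12% risk of loss by Week 52 (hazard per visit 1 − 0.88^(1/4) = 3.15%). Affected subjects are last assessed at Week 36. Overstatement of the 88% true maintenance over that interval, in percentage points:

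| Affected subjects stop at | 15 affected | 5 affected |
|---|---|---|
| Week 52 (all) | 1.38 | 0.46 |
| Week 50 (all) | 1.0 | 0.34 |
| Spread over Weeks 36-52 | 0.57 | 0.23 |
| Week 41 (all) | 0.33 | 0.11 |

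The top-left entry equals the simple dilution: 0.12 × 115/130 = 10.6% estimated loss against 12%, a gap of 1.4 points. It needs all 15 to remain at risk and unassessed through the last event time.

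**Not a strict bound.** Putting 20 affected subjects into the example in step 1 (110 in total, 18% affected, all with the 14-week gap) gives 79.5% against 77.7%, a difference of 1.8 points. Many affected subjects with uniformly long gaps would exceed 1.4.

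**The case against.** The strongest reply is that the Protocol already closes the gap for many of these subjects. sPGA and PASI are scheduled at the early-discontinuation visit, and subjects who stop are asked to keep attending. A subject assessed at discontinuation has in effect returned: a loss found there takes the midpoint rule, and if there is none, response is confirmed at about the stop date and censoring there is right. This stands, and it limits the problem to subjects without that assessment. A reader might infer that every subject who misses visits and then stops is mishandled; the documents do not support that. The reply does not remove the problem, because the SAP rule does not depend on that assessment having been done.

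Second, long unassessed gaps on treatment may be uncommon. Drug is dispensed at each visit from Week 24 to Week 48, in four-week kits (Protocol Table 3 and 6.2), and the visible text gives no supply route for subjects who miss visits. If whole visits were missed, stopping would tend to follow soon after the last one, which points to the low end of the range. Visits where only the efficacy assessment was missed could give longer gaps. The documents give no numbers for either case.

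Third, a reader might infer that the bias helps a confirmatory claim for the drug. It does not. Time to first loss is not among the coprimary or key secondary endpoints in SAP 4.1, nor in the visible planned-analysis list in SAP Appendix 1. Protocol 9.4.4 describes a curve for one arm, without a comparator.

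Fourth, parts of the SAP efficacy section are not visible, and a general censoring rule may stand there. That is a fair caution, but the COVID-19 rule in 6.6.1 is explicit for these subjects.

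**Conclusion.** The point holds as a minor one. As written, 6.6.1 counts unassessed time as maintained response for affected subjects who have no early-discontinuation sPGA/PASI, and the effect on the two Kaplan-Meier curves is upwards. Its size cannot be known from the documents. Roughly 0.1 to 1.4 percentage points is a reasonable range under the assumed inputs (2-20% of responders affected, 70-85% true maintenance, varying stop times). It should not be read as 1.4 points expected, since that end needs everyone affected to stay unassessed until Week 52. Only the description of maintenance on BMS-986165 changes.

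**What to change.** In SAP 6.6.1, replace the censoring date for these subjects with the date of the last efficacy assessment at which response was still present. State that an sPGA/PASI done at early discontinuation counts as that assessment if response is maintained, and that a loss found there follows the midpoint rule already given.

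The cost is one phrase and slightly shorter follow-up for a few subjects. The change does not remove all bias: if affected subjects lose response faster than others, the estimate remains somewhat high, as the simulation shows. A sensitivity analysis that counts stopping after an unassessed gap as a loss, or that uses interval-censored methods, would show how much this matters.
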